9.5.1.5.3 LABORATORY MEASUREMENTS

Clinical laboratory tests to be performed, including hematology, chemistry, urinalysis, and CSF are summarized in [Table 4](#). Subjects should be in a seated or supine position during blood collection. [Table 6](#), [Table 7](#), and [Table 14](#) show the visits and time points at which blood for clinical laboratory tests and urine for urinalysis will be collected in the study. (revised per Amendment 07)

See [Section 9.3.3](#) for safety criteria for discontinuation from study drug-related to absolute counts of CD4, CD8, and B lymphocytes, and for lymphocyte subset counts. See [Appendix 6](#) for safety criteria for discontinuation from study drug related to absolute lymphocyte counts.

Table 4 Clinical Laboratory Tests

| Category | Parameters |
|-----------------------------|--|
| Hematology | Hematocrit, hemoglobin, platelets, red blood cell count, and white blood cell count with differential (bands, basophils, eosinophils, lymphocytes, monocytes, neutrophils). PT, PTT, and INR (Screening, Baseline, and Visit 21 only) (revised per Amendment 02 and 07) |
| Chemistry | |
| Electrolytes | Bicarbonate, calcium, chloride, phosphate, potassium, sodium |
| Liver function tests | Alanine aminotransferase, alkaline phosphatase, aspartate aminotransferase, gamma glutamyl transpeptidase, direct bilirubin, total bilirubin |
| Renal function tests | Blood urea/blood urea nitrogen, creatinine |
| Other | Albumin, cholesterol, globulin, glucose, lactate dehydrogenase, total protein, triglycerides, uric acid |
| Urinalysis | Bacteria, casts, crystals, epithelial cells, glucose, ketones, occult blood, pH, protein, red blood cells, specific gravity, white blood cells |
| Other | Lymphocyte T and B cell subset analyses (see Table 5). Regulatory T cells (revised per Amendment 04) PBMCs (revised per Amendment 02) Ig analyses (IgG, IgA, and IgM). Viral screen (HCVAb [Hepatitis C] and HbsAg [Hepatitis B]). Viral characterization (including HSV1, HSV2 and CMV, etc.) Serum pregnancy test (females of child bearing potential only) Tuberculosis Interferon Gamma Release Assays Tests for thyroid function (thyroid stimulating hormone, free triiodothyronine and free thyroxin) and vitamin B12 Blood sample for storage for subsequent testing of immune status Cerebrospinal fluid sampling |

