9.7.1.8.3 LABORATORY VALUES

Laboratory results will be summarized using International System of Units, as appropriate. For all quantitative parameters listed in [Section 9.5.1.5.3](#), the actual value and the change from baseline to each postbaseline visit and to the end of treatment (defined as the last on-treatment value) will be summarized by visit and treatment group using descriptive statistics. Qualitative parameters listed in [Section 9.5.1.5.3](#) will be summarized using frequencies (number and percentage of subjects), and changes from baseline to each postbaseline visit and to end of treatment will be reported using shift tables. Percentages will be based on the number of subjects with both nonmissing baseline and relevant postbaseline results.

Laboratory test results will be assigned a low/normal/high (LNH) classification according to whether the value was below (L), within (N), or above (H) the laboratory parameter's reference range. Within-treatment comparisons for each laboratory parameter will be based on 3-by-3 tables (shift tables) that compare the baseline LNH classification to the LNH classification at each postbaseline visit and at the end of treatment. Similar shift tables will also compare the baseline LNH classification to the LNH classification for the highest and lowest value during the Treatment Period.

[Appendix 1](#) (Sponsor's Grading for Laboratory Values) presents the criteria that will be used to identify subjects with treatment-emergent markedly abnormal laboratory values (TEMAVs). Except for phosphate, a TEMAV is defined as a postbaseline value with an increase from baseline to a Grade of 2 or higher. For phosphate, a TEMAV was defined as a postbaseline value with an increase from baseline to a Grade of 3 or higher. When displaying the incidence of TEMAVs, each subject may be counted once in the laboratory parameter high and in the laboratory parameter low categories, as applicable.

Lymphocyte subsets measured (including but not limited to CD4 [T helper cells], CD8 [cytotoxic T cells], CD19 [B cells], CD16/CD56 [natural killer cells] and CD14 [macrophages] and regulatory T cells) will be summarized in the same manner as other laboratory parameters. Mean lymphocyte subsets and the mean change from baseline in lymphocyte subsets will also be displayed graphically over time by dose.

Serum IgG, IgM, and IgA will be measured and summarized in the same manner as other laboratory parameters.

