| Calcium, serum-low (hypocalcemia) (conversion to mmolx0.25) | <8.5 – 8.0 mg/dL <2.13 – 2.0 mmol/L | <8.0 – 7.0 mg/dL <2.0 – 1.75 mmol/L | <7.0 – 6.0 mg/dL <1.75 – 1.5 mmol/L | <6.0 mg/dL <1.5 mmol/L |
| Calcium, serum-high (hypercalcemia) | >10.6 – 11.5 mg/dL >2.65 – 2.9 mmol/L | >11.5 – 12.5 mg/dL >2.9 – 3.1 mmol/L | >12.5 – 13.5 mg/dL >3.1 – 3.4 mmol/L | >13.5 mg/dL >3.4 mmol/L |
| Cholesterol, serum-high (hypercholesterolemia) (conversion to mmol/L x0.02586) | 0 - 19 years >169 – 300 mg/dL >4.37 – 7.75 mmol/L 19 - 150 years >199 – 300 mg/dL >5.15 – 7.75 mmol/L | >300 – 400 mg/dL >7.75 – 10.34 mmol/L | >400 – 500 mg/dL >10.34 – 12.92 mmol/L | >500 mg/dL >12.92 mmol/L |
| Creatinine | Female >1.00 mg/dL – 1.5x1.00 Male >1.27 mg/dL – 1.5x1.27 | Female >1.5 – 3.0x1.00 Male >1.5 mg/dL – 3.0x1.27 | Female >3.0 – 6.0x1.00 Male >3.0 mg/dL – 6.0 x1.27 | Female >6.0x1.00 Male >6.0x1.27 |
| Gamma glutamyl transpeptidase | Female >60 IU/L – 3.0x60 Male >65 IU/L – 3.0x65 | Female >3.0 – 5.0x60 Male >3.0 – 5.0x65 | Female >5.0 – 20.0x60 Male >5.0 – 20.0x65 | Female >20.0x60 Male >20.0x65 |
| Glucose, serum-high (hyperglycemia) (conversion to mmol/L x0.0555) | Fasting glucose value >99 – 160 mg/dL >5.5 – 8.9 mmol/L | Fasting glucose value >160 – 250 mg/dL >8.9 – 13.9 mmol/L | >250 – 500 mg/dL; >13.9 – 27.8 mmol/L; hospitalization indicated | >500 mg/dL; >27.8 mmol/L; life-threatening consequences |
| Glucose, serum-low (hypoglycemia) | <65 – 55 mg/dL <3.6 – 3.0 mmol/L | <55 – 40 mg/dL <3.0 – 2.2 mmol/L | <40 – 30 mg/dL <2.2 – 1.7 mmol/L | <30 mg/dL <1.7 mmol/L life-threatening consequences; seizures |
| Phosphate, serum-low (hypophosphatemia) (conversion to mmol/L x0.323) | not applicable | <2.5 – 2.0 mg/dL <0.8 – 0.6 mmol/L | <2.0 – 1.0 mg/dL <0.6 – 0.3 mmol/L | <1.0 mg/dL <0.3 mmol/L life-threatening consequences |
| Potassium, serum-high (hyperkalemia) | not applicable | >5.5 – 6.0 mmol/L | >6.0 – 7.0 mmol/L hospitalization indicated | >7.0 mmol/L life-threatening consequences |
| Potassium, serum-low (hypokalemia) | <3.5 mEq/L – 3.0 mmol/L | <LLN – 3.0 mmol/L; symptomatic; intervention indicated | <3.0 – 2.5 mmol/L hospitalization indicated | <2.5 mmol/L life-threatening consequences |
| Sodium, serum-high (hypernatremia) | >144 mEq/L – 150 mmol/L | >150 – 155 mmol/L | >155 – 160 mmol/L hospitalization indicated | >160 mmol/L life-threatening consequences |

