| Sodium, serum-low (hyponatremia) | <134 mEq/L – 130 mmol/L | Not applicable | <130 – 120 mmol/L | <120 mmol/L life-threatening consequences |
| Triglyceride, serum-high (hypertriglyceridemia) | 150 – 300 mg/dL 1.71 – 3.42 mmol/L | >300 – 500 mg/dL >3.42 – 5.7 mmol/L | >500 – 1000 mg/dL >5.7 – 11.4 mmol/L | >1000 mg/dL >11.4 mmol/L life-threatening consequences |

| | Grade 1 | Grade 2 | Grade 3 | Grade 4 |
|---------------------------------------|--|----------------|--|--|
| Uric acid, serum-high (hyperuricemia) | Female >7.1 – 10 mg/dL Male >8.6 – 10 mg/dL Both ≤0.59 mmol/L without physiologic consequences | Not applicable | Female >7.1 – 10 mg/dL Male >8.6 – 10 mg/dL Both ≤0.59 mmol/L without physiologic consequences | >10 mg/dL >0.59 mmol/L life-threatening consequences |

LLN = lower limit of normal, ULN = upper limit of normal.

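### Appendix 1 prints the same uric acid criterion for Grade 1 and Grade 3, so moderately raised values both count and do not count as markedly abnormal; male creatinine carries a lesser unit slip

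*Protocol*

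**What the plan says.** Protocol Section 9.7.1.8.3 names Appendix 1 as the source of the TEMAV criteria and sets the rule: "Except for phosphate, a TEMAV is defined as a postbaseline value with an increase from baseline to a Grade of 2 or higher". Phosphate, the one exception, needs Grade 3.

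Uric acid is a planned chemistry test. Table 4 in Section 9.5.1.5.3 lists "lactate dehydrogenase, total protein, triglycerides, uric acid".

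In the Appendix 1 uric acid row, the Grade 1 cell reads "Female >7.1 – 10 mg/dL Male >8.6 – 10 mg/dL Both ≤0.59 mmol/L without physiologic consequences". Grade 2 is marked as not applicable. The Grade 3 cell repeats the Grade 1 text word for word. Grade 4 starts above 10 mg/dL.

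In the creatinine row, the male cells read:
- Grade 1: "Male >1.27 mg/dL – 1.5x1.27"
- Grade 2: "Male >1.5 mg/dL – 3.0x1.27"
- Grade 3: starts at "Male >3.0 mg/dL" and ends at 6.0 times 1.27
- Grade 4: "Male >6.0x1.27"

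**The concern.** A grading table used to classify results must put each value in one grade. The uric acid row does not, and the two grades it assigns fall on opposite sides of the TEMAV cut. Whoever programs the table has to choose. Using the Grade 3 cell, every new value above 7.1 mg/dL (women) or 8.6 mg/dL (men) is reported as a Grade 3 markedly abnormal result. Using the Grade 1 cell, nothing is reported until the value passes 10 mg/dL.

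Laboratory parameters are part of the primary safety endpoint (Section 9.7.1.1.1), and the target is about 15 subjects per arm (Section 9.7.2). One reclassified subject moves an arm's TEMAV incidence by 1/15, about 6.7 percentage points.

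The male creatinine row shows a related fault: two lower limits are printed as absolute concentrations where the rest of the row works in multiples of the upper limit of normal.

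**Working it through.** The plan states no figure to reproduce. The check is whether the printed grade intervals overlap, and whether an overlap crosses the line between Grade 1 and Grade 2. Each interval is read as above the lower limit, up to and including the upper limit.

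**Uric acid, as printed (mg/dL)**

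| | Grade 1 | Grade 2 | Grade 3 | Grade 4 |
|---|---|---|---|---|
| Female | >7.1 to 10 | none | >7.1 to 10 | >10 |
| Male | >8.6 to 10 | none | >8.6 to 10 | >10 |

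The clinical qualifier in Grades 1 and 3 is also the same, so it does not separate them. The whole Grade 1 band is also Grade 3. The two possible TEMAV starting points differ by:
- female: 10 / 7.1 = 1.41-fold
- male: 10 / 8.6 = 1.16-fold

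**Male creatinine, read literally (mg/dL)**

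- Grade 1: >1.27 to 1.5 × 1.27 = 1.905
- Grade 2: >1.5 to 3.0 × 1.27 = 3.81
- Grade 3: >3.0 to 6.0 × 1.27 = 7.62
- Grade 4: >7.62

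Overlaps:
- Grades 1 and 2: >1.5 to 1.905, width 1.905 − 1.5 = 0.405. This crosses the TEMAV line. The literal start is 1.5 / 1.27 = 1.18 times the upper limit, where 1.5 times was meant.
- Grades 2 and 3: >3.0 to 3.81, width 3.81 − 3.0 = 0.81. Both are TEMAV grades for anyone starting at or below Grade 1, so for them only the grade shown changes.

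The literal reading can also remove TEMAVs. A man at 1.6 mg/dL at baseline and 2.0 mg/dL later rises from Grade 1 to Grade 2 under the intended limits. If his baseline is taken as Grade 2, there is no increase.

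**Female creatinine.** The reference limit is 1.00, so absolute limits and multiples coincide and nothing overlaps.

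**After correction.** With the male limits as multiples of 1.27 (1.905, 3.81, 7.62), a scan from 1 to 12 mg/dL in steps of 0.001 finds no value in two grades. For uric acid, the overlap disappears only once Grade 3 carries a criterion different from Grade 1.

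**Comparison with other Appendix 1 rows.** Low sodium also leaves Grade 2 empty but gives Grade 3 its own range. Low potassium uses essentially one range for Grades 1 and 2 and separates them by symptoms and need for intervention. Uric acid has neither a separate range nor a separate qualifier.

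**The case against.** The strongest reply is that both faults are editorial and their intended meaning can be recovered.

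For creatinine this largely stands. The table regularly leaves the multiplier off the lower limit; the gamma glutamyl transpeptidase row, for example, has "Male >3.0 – 5.0x65", and nobody would start Grade 2 there at 3 units. Male creatinine Grade 1 ends, and Grade 4 begins, at a multiple of 1.27. The unit after 1.5 and 3.0 is a slip, and calling the row truly ambiguous would overstate it.

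For uric acid the reply stands only in part. Given the qualifiers in Grades 1 and 4, a miscopied Grade 3 qualifier is the likely explanation, and the low potassium row shows the pattern it would follow. But the protocol does not print the intended qualifier. A separate Grade 2 cell stands between the two identical ones, so a merged cell is an unlikely cause.

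It can also be said that TEMAV programming belongs in the SAP, which is not shown. The SAP may well settle it. However, the protocol itself fixes Appendix 1 as the rule, so the error is in this document.

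Finally, the effect is narrow. Change-from-baseline summaries and the low/normal/high shift tables do not use these grades, and under Section 9.5.1.5.1 the investigator still reviews all laboratory findings for adverse event status. That stands and limits the severity.

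**Conclusion.** The uric acid row is wrong as written: one criterion serves a grade below the TEMAV cut and a grade above it. The size is the difference between starting at 7.1 or 10 mg/dL in women and at 8.6 or 10 mg/dL in men. The male creatinine fault is secondary, with an obvious correction; taken literally it lowers the TEMAV start from 1.905 to 1.5 mg/dL. The consequence is confined to descriptive TEMAV incidence for two analytes, so the point is minor. The documents give no distribution of either analyte, so the number of subjects affected cannot be computed.

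Two stronger readings are not supported. A reader might infer that a hypothesis test or a Core Study discontinuation rule is compromised; none depends on the uric acid or creatinine grades.

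A reader might also link this to the Extension Phase lymphocyte rule in Appendix 6, item 1, which interrupts drug below the higher of 800/mm³ and the lower limit of normal but permits restart above the lower limit alone. That is a dosing matter separate from TEMAV grading. It becomes a gap only if the lower limit, which is not stated, is below 800/mm³. Its consequence would not be merely another interruption either: a second confirmed count below 800/mm³ within 6 months leads to permanent discontinuation. Calling counts below 800/mm³ Grade 2 there, against below 700/mm³ in Appendix 1, is a labelling difference, because Appendix 6 gives its own cut-off.

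**What to change.** **Uric acid.** State that values above 7.1 (female) or 8.6 (male) up to 10 mg/dL without physiologic consequences are Grade 1 only and are not TEMAVs. Change the Grade 3 qualifier to with physiologic consequences, as the low potassium row separates a shared range by clinical status. Start TEMAV counts that rest on laboratory values alone above 10 mg/dL, taking the numeric Grade 4 limit as sufficient. The wording of the qualifier is inferred from the table's pattern, so the sponsor should confirm it.

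**Male creatinine (mg/dL).** Keep Grade 1 at >1.27 to 1.905 and Grade 4 at >7.62. Print Grade 2 as >1.5 × 1.27 to 3.0 × 1.27 (>1.905 to 3.81) and Grade 3 as >3.0 × 1.27 to 6.0 × 1.27 (>3.81 to 7.62).

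**Cost.** Text corrections to two table rows and matching TEMAV programming, with no new data. The small downside is that a uric acid value up to 10 mg/dL with clinical consequences would appear as an adverse event and not in the TEMAV table.

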Appendix 2 List of Permitted and Prohibited Prior/Concomitant Medications

Prohibited medications are shown in [Listing 1](#) through [Listing 5](#). Medications permitted with restrictions are listed in [Listing 6](#) through [Listing 8](#). (revised per Amendment 04) **These may not be all-inclusive listings.** Please contact the medical monitor(s) if the investigators have any questions or concerns regarding any medication not listed that your subjects may be taking before enrollment or start during the course of the E2609-G000-202 study.

Antibiotics, analgesics, and anti-inflammatory drugs intended for short courses of treatment are permitted and do not need to follow the restrictions of [Listing 8](#) for a stable dose of 4 weeks before Baseline. If these medications may affect cognitive function but the medications are clinically indicated, then cognitive testing should not take place until at least 72 hours after the last dose of the course of treatment.

Prohibited Prior/Concomitant Medications

Listing 1 Drugs with High Risk of Torsades de Pointes or QTc Prolongation

| Generic name | Brand name (Names shown are not exhaustive and are examples only; names may be the ® or ™) | Comments |
|---|--|---|
| Prohibited from 14 days (or 5 half-lives, whichever is longer) before Randomization until after the last treatment visit | | |
| Anti-arrhythmic/ abnormal heart rhythm | | |
| Amiodarone | Cordarone; Pacerone | Incidence in females greater than males, Torsades de Pointes risk regarded as low |
| Disopyramide | Norpace | Incidence in females greater than males |
| Dofetilide | Tikosyn | |
| Ibutilide | Corvert | Incidence in females greater than males |
| Procainamide | Pronestyl; Procan | |
| Quinidine | Cardioquin; Quinaglute | Incidence in females greater than males |
| Sotalol | Betapace | Incidence in females greater than males |
| Antihistamine/ allergic rhinitis | | |
| Astemizole | Hismanal | No longer available in United States |
| Terfenadine | Seldane | No longer available in United States |
| Anti-anginal/ heart pain | | |
| Bepridil | Vascor | Incidence in females greater than males |
| Antibiotic/ bacterial infection | | |
| Clarithromycin | Biaxin | |
| Moxifloxacin | Avelox | |
| Sparfloxacin | Zagam | |
| Listing 1 continued | | |
| Antimalarial/ malaria infection | | |
| Chloroquine | Aralen | |
| Halofantrine | Halfan | Incidence in females greater than males |
| Antipsychotic/ anti-emetic/ schizophrenia/ nausea | | |
| Chlorpromazine | Thorazine | |
| Gastrointestinal stimulant/ heartburn | | |
| Cisapride | Propulsid | |

Listing 1 Drugs with High Risk of Torsades de Pointes or QTc Prolongation

| Generic name | Brand name (Names shown are not exhaustive and are examples only; names may be the ® or ™) | Comments |
|--|--|---|
| Antinausea/ nausea | | |
| Domperidone | Motillum | Not available in the United States |
| Sedative; antinausea/ anesthesia adjunct, nausea | | |
| Droperidol | Inapsine | |
| Antibiotic; gastrointestinal stimulant/ bacterial infection; increase gastrointestinal motility | | |
| Erythromycin | Erythrocin; E.E.S. | Incidence in females greater than males |
| Antipsychotic/ schizophrenia | | |
| Haloperidol | Haldol | When given intravenously or at higher than recommended doses, risk of sudden death, QT prolongation, and torsades increases |
| Mesoridazine | Serentil | |
| Thioridazine | Mellaril | |
| Opiate agonist/ pain control, narcotic dependence | | |
| Levomethadyl | Orlaam | |
| Methadone | Methadose; Dolophine | Incidence in females greater than males |
| Anti-infective/ pneumocystis pneumonia | | |
| Pentamidine | Pentam; NebuPent | Incidence in females greater than males |
| Antipsychotic/ Tourette's tics | | |
| Pimozide | Orap | Incidence in females greater than males |
| Antilipemic/ hypercholesterolemia | | |
| Probucol | Lorelco | No longer available in United States |
| Anticancer | | |
| Arsenic trioxide | Trisenox | Used for leukemia |
| Vandetanib | Zactima | Used for thyroid cancer |

Note: This list is not exhaustive.

QTc = Corrected QT interval.

Listing 2 Prohibited Medications Within 5 Half-lives or 60 days, Whichever is Longer, Before Randomization and Until after the Last Treatment Visit

| Generic name | Brand name (Names shown are not exhaustive and are examples only; names may be the ® or ™) |
|---|--|
| Systemic Immunosuppressants^{a,b} and Immunomodulatory therapy | |
| Azathioprine | Azasan, Imur |
| Ciclosporine | Gengraf, Neoral |
| Dexamethasone | Decadron, Dexasone, Diodex, Hexadrol, Maxidex |
| Fingolimod | Gilenya |
| Methotrexate | Trexall |
| Methylprednisolone | Medrol, Meprolone |
| Mycophenolate | CellCept, Myfortic |
| Prednisolone | Deltasone, Prednicot, Prednisone Intensol, Rayos, Sterapred, Sterapred DS |

Note: This list is not exhaustive.

- a: Topical and inhaled formulations with minimal systemic exposure need not be prohibited.
- b: During the Treatment Period of the study, short term (not more than 14 days) use of steroids up to the equivalent of prednisolone 40 mg QD is permitted after discussion with the medical monitor. Dosing with study drug should be suspended from the time steroid treatment is started. Complete blood count and lymphocyte subsets (for Core Study and the first 12 months of Extension Phase only) should be determined before starting steroid treatment and continue to be monitored weekly. (revised per Amendment 08) Study drug may be resumed after discussion with the medical monitor when the following conditions are met: (1) treatment with steroids has been completed for at least 1 week; (2) absolute lymphocytes not <LLN; (3) no lymphocyte subsets are below the discontinuation threshold (for Core Study only); (4) the investigator considers that the medical condition which required treatment with steroids has improved or resolved. Weekly testing of lymphocyte subset counts (for Core Study only) and CBC with differentials is required for 4 weeks following resumption of study drug administration. (revised per Amendment 04)

Listing 3 Prohibited Medications Within 6 Months Before Randomization

| Generic name | Brand name (Names shown are not exhaustive and are examples only; names may be the [®] or [™]) |
|---|---|
| Immunoglobulin therapy | |
| Adalimumab | Humira |
| Bevacizumab | Avastin |
| Efalizumab | Raptiva |
| Etanercept | Enbrel |
| Immune globulin IV, IVIG, IGIV | Carimune, Flebogamma, Gamimune N, Gammagard, Gamunex, Gammar-P IV, Iveegam, Octagam, Panglobulin, Vigam, Polygam S/D, Privigen, Sandoglobulin, Venoglobulin-S |
| Infliximab | Remicade |
| Omalizumab | Xolair |
| Ranibizumab | Lucentis |
| Other monoclonal antibodies not listed here | |

Note: This list is not exhaustive.

Listing 4 Prohibited Live Vaccines Within 3 Months Before Randomization Until after the Last Treatment Visit (this does not apply to non-live/inactivated vaccines)

| Bacterial vaccines | Viral vaccines |
|---|---|
| Bacillus Calmette-Guérin vaccine against tuberculosis | Measles vaccination |
| Cholera vaccination (oral) | Rubella vaccination |
| | Oral polio vaccination (Sabin) |
| | Yellow fever vaccination |
| | Varicella (chickenpox) vaccination |
| | Rotavirus vaccination |
| | Japanese encephalitis vaccination |
| | Live attenuated influenza vaccine (FluMist, Fluenz) |
| Typhoid vaccination (oral) | Mumps vaccination |

Note: This list is not exhaustive

**Listing 5 Strong CYP3A4 Inhibitors Prohibited Within 5 Half-Lives or 14 Days
(Whichever Is Longer) Before Randomization Until After the Last Treatment Visit**

| Generic name | Brand name(s) |
|---------------------|--|
| boceprevir | Victrelis |
| clarithromycin | Clarithromycin, clarithromycin extended release, Prevpac |
| cobicistat | Tybost, Stribild, |
| conivaptan | Vaprisol |
| danoprevir | |
| elvitegravir | Vitekta, Stribild |
| indinavir | Crixivan |
| itraconazole | Sporanox, Onmel |
| ketoconazole | Xolegel, Nizoral, Ketodan |
| lopinavir | Kaletra |
| nefazodone | Serzone |
| nelfinavir | Viracept |
| posaconazole | Noxafil |
| ritonavir | Norvir, Kaletra |
| saquinavir | Invirase, Fortovase |
| telaprevir | Incivek |
| telithromycin | Ketek |
| tipranavir | Aptivus |
| troleandomycin | Triocetin |
| voriconazole | Vfend, Voriconazole |

Note: This list is not exhaustive

Permitted Prior/Concomitant Medications

Listing 6 Medications Which Need To Be on a Stable Dose for 12 Weeks Before the Baseline Cognitive Assessments at Visit 2 and Remain on the Same Stable Dose from Baseline to Final Follow-Up Visit

| Generic name | Brand name (Names shown are not exhaustive and are examples only; names may be the [®] or [™]) |
|----------------------------|---|
| Cognitive Enhancers | |
| Donepezil | Aricept |
| Galantamine | Reminyl |
| Memantine | Namenda |
| Rivastigmine | Exelon |

Note: This list is not exhaustive.

Listing 7 Permitted Medications Used on PRN Basis Which are Not to be Used Within 72 Hours before Cognitive Testing

| Generic name | Brand name (Names shown are not exhaustive and are examples only; names may be the ® or ™) |
|---|---|
| Opiates | |
| Morphine | Astramorph PF, Avinza, Depo Dur, Duramorph, Infumorph, Kadian, MS Contin, MSIR, Oramorph SR, RMS, Roxanol |
| Opiate Agonists | |
| Codeine | Codeine |
| Fentanyl | Actiq, Duragesic, Fentora, Onsolis, Sublimaze |
| Meperidine | Demerol, Meperitab |
| Oxycodone | Dazidox, Endocodone, Eth-OxyDose, OxyContin, OxyFast, OxyIR, Percolone, Roxicodone, Roxicodone Intensol |
| Other opioids or opioid agonists which are used on PRN basis | |
| Benzodiazepines and sedatives | |
| Alprazolam | Alprazolam Intensol, Niravam, Xanax |
| Amitriptyline | (various) |
| Chlordiazepoxide | H-Tran, Librium |
| Clonazepam | Ceberclon, Klonopin |
| Diazepam | Diastat, Dizac, Valium |
| Dothiepin | (various) |
| Estazolam | ProSom |
| Flunitrazepam | Rohypnol |
| Flurazepam | Dalmane |
| Lorazepam | Ativan |
| Midazolam | Versed |
| Olanzapine | Zyprexa |
| Promethazine | Phenergan; others |
| Ramelteon | Rozerem |
| Risperidone | Risperdal |
| Temazepam | Restoril |
| Triazolam | Halcion |
| Zolpidem | Ambien; others |
| Zopiclone | (various) |
| Other benzodiazepines, tricyclic antidepressants, antipsychotics and other drugs which are used on PRN basis as sedatives | |

Note: This list is not exhaustive

PRN = Pro re nata

Listing 8 Permitted Centrally Active or Psychiatric Medications

| Generic Name | Brand name (Names shown are not exhaustive and are examples only; names may be the ® or ™) |
|---|--|
| If to be used on a PRN basis see Listing 7. If to be used chronically, subjects must be on a stable dose for ≥4 weeks before Baseline. Changes in dose or initiation of new concomitant medications for chronic use (not PRN use) is permitted but if the medication affects cognitive function, do not conduct cognitive testing until the dose is stable for 4 weeks. | |
| Antidepressants | |
| Amitriptyline hydrochloride | Elavil |
| Amoxapine | Amoxapine |
| Bupropion | Aplenzin, Budeprion, Buproban, Zyban, Wellbutrin |
| Citalopram | Celexa |
| Clomipramine hydrochloride | Anafranil |
| Desipramine hydrochloride | Norpramin |
| Desvenlafaxine | Pristiq |
| Doxepin hydrochloride | Prudoxin, Silenor, Sinequan, Zonalon |
| Duloxetine | Cymbalta |
| Escitalopram | Lexapro |
| Fluoxetine | Prozac, Sarafem, Selfemra |
| Fluvoxamine | Luvox |
| Imipramine hydrochloride | Tofranil |
| Isocarboxazid | Marplan |
| Maprotiline hydrochloride | Ludiomil |
| Mirtazapine | Remeron Soltab |
| Nortriptyline hydrochloride | Aventyl, Pamelor |
| Paroxetine | Paxil, Pexeva |
| Phenelzine | Nardil |
| Protriptyline hydrochloride | Vivactil |
| Rasagiline | Azilect |
| Selegiline | EMSAM |
| Sertraline | Sertaraline, Zoloft |
| Tranlycypromine | Parnate |
| Trazodone hydrochloride | Desyrel, Oleptro |
| Trimipramine maleate | Surmontil |
| Venlafaxine hydrochloride | Effexor |

Listing 8 Permitted Centrally Active or Psychiatric Medications

| Generic Name | Brand name (Names shown are not exhaustive and are examples only; names may be the ® or ™) |
|---|--|
| Mood Stabilizers (Listing 8 continued) | |
| Carbamazepine | Carbatrol, Epitol, Equetro, Tegretol, Tegretol XR |
| Lamotrigine | Lamictal, Lamictal CD, Lamictal ODT, Lamictal XR |
| Valproic acid | Depacon, Depakene, Depakote, Depakote ER, Divalproex Sodium, Stavzor, Valproate |
| Antipsychotics | |
| Acetophenazine | Tindal |
| Aripiprazole | Abilify |
| Asenapine | Saphris |
| Olanzapine | Zyprexa |
| Chlorpromazine | Thorazine |
| Haloperidol | Haloperidol, Haldol |
| Clozapine | Clozaril, Fazaclo |
| Fluphenazine | Prolixin |
| L-Methylfolate | Deplin, L-Methylfolate Calcium |
| Loxapine | Loxitane |
| Mesoridazine | Serentil |
| Perphenazine | Trilafon |
| Quetiapine | Seroquel |
| Risperidone | Risperdal |
| Thioridazine | Mellaril |
| Thiothixene | Navane |
| Trifluoperazine | Stelazine |
| Benzodiazepines | |
| Alprazolam | Alprazolam Intensol, Niravam, Xanax |
| Chlordiazepoxide | H-Tran, Librium |
| Clonazepam | Ceberclon, Klonopin |
| Diazepam | Diastat, Dizac, Valium |
| Estazolam | ProSom |
| Flunitrazepam | Rohypnol |
| Flurazepam | Dalmane |
| Lorazepam | Ativan |

Listing 8 Permitted Centrally Active or Psychiatric Medications

| Generic Name | Brand name (Names shown are not exhaustive and are examples only; names may be the ® or ™) |
|--------------|--|
| Midazolam | Versed |
| Temazepam | Restoril |
| Triazolam | Halcion |
| Zopiclone | Imovane, Zimovane |
| Zopidem | Ambien, Ambien CR, Intermezzo, Stilnox, Stilnoct, Sublinox, Hypnogen, Zolsana |

Note: This list is not exhaustive.

PRN = Pro re nata

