9.4.7 Prior and Concomitant Therapy

Medication (including over-the-counter medications) or therapy administered to the subject before the study (within 6 months of randomization) and during the study (starting at the date of informed consent) will be recorded on the Prior & Concomitant Medication eCRF or Non-Pharmacological Procedures eCRF. The investigator will record on the Adverse Event eCRF any AE for which the concomitant medication/therapy was administered. If the concomitant medication/therapy is being administered for a medical condition present at the time of entry into the study, the investigator will record the medical condition on the Medical History and Current Medical Condition eCRF.

Listings of prohibited and permitted drugs during the Core Study and Extension Phase are provided in [Appendix 2](#). (revised per Amendment 07) Prohibited medications are presented in [Listing 1](#) through [Listing 5](#). Medications that are permitted with restrictions are listed in [Listing 6](#) through [Listing 8](#). (revised per Amendment 04)

The types of agents listed below are not permitted before randomization unless discontinued according to the specific timeframes as shown below; these types of agents are not permitted during the Core Study or Extension Phase until after the last treatment visit: (revised per Amendments 04 and 07)

- Drugs which may cause QTc prolongation are not permitted for a period of 5 half-lives or 14 days (whichever is longer) before randomization
- Strong CYP3A4 inhibitors are not permitted for a period of 5 half-lives or 14 days (whichever is longer) before randomization
- Live vaccines are not permitted within 3 months before randomization. This does not apply to non-live/inactivated vaccines

- Ig therapy and biologic drugs are not permitted within 6 months before randomization

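### Appendix 2 both prohibits and permits four QT-prolonging antipsychotics; the Listing 8 entries are the error and should be deleted

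*Protocol*

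**What the plan says.** The introduction to Appendix 2 divides its listings in two: Listings 1 to 5 are prohibited, and Listings 6 to 8 are permitted with restrictions.

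- **Listing 1** (high risk of torsades de pointes or QTc prolongation) carries the rule "Prohibited from 14 days (or 5 half-lives, whichever is longer) before Randomization until after the last treatment visit". It names chlorpromazine, haloperidol, mesoridazine and thioridazine. Haloperidol has the comment "When given intravenously or at higher than recommended doses, risk of sudden death, QT prolongation, and torsades increases"; the other three have none.
- **Listing 8** (permitted centrally active or psychiatric medications) names the same four under Antipsychotics, including "Haloperidol | Haloperidol, Haldol". Its header asks for a stable dose for at least 4 weeks before Baseline in chronic use, and adds "Changes in dose or initiation of new concomitant medications for chronic use (not PRN use) is permitted", with a condition about cognitive testing only. It sends as-needed use to Listing 7.
- **Listing 7** ends its sedative block with a general row: "Other benzodiazepines, tricyclic antidepressants, antipsychotics and other drugs which are used on PRN basis as sedatives".
- **Section 9.4.7** states "Drugs which may cause QTc prolongation are not permitted for a period of 5 half-lives or 14 days (whichever is longer) before randomization" and extends that bar through the Core Study and Extension Phase until after the last treatment visit. It names no such drug. For names it says "Listings of prohibited and permitted drugs during the Core Study and Extension Phase are" in Appendix 2.
- **Section 9.3.2**: criterion 25 excludes users of QT-prolonging medication, and criterion 37 excludes breaches of the medication restrictions.

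**The concern.** A site that wants to know whether a patient may take, say, haloperidol has to look in Appendix 2, because that is where the Protocol names the drugs. Appendix 2 gives both answers and has no rule for choosing between them. A site that reads only Listing 8 could keep a patient on one of these drugs, or start one, in good faith.

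The Protocol treats QT as a real safety matter. ECG parameters are part of the primary endpoint (Section 9.7.1.1.1), and Section 9.3.3 has QTcF stopping rules for the Core Study. Appendix 6 keeps one for the Extension Phase (a rise of more than 60 msec together with QTcF above 450 msec) and makes QTcF above 500 msec a matter for discussion with the medical monitor. A banned co-medication taken in error exposes the patient to the risk that the ban is meant to prevent. Its QT effect could also trigger a stop or be attributed to elenbecestat.

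**Working it through.** **1. Set the listings side by side.**

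| Drug | Listing 1 | Listing 8, Antipsychotics |
|---|---|---|
| Chlorpromazine | prohibited | permitted |
| Haloperidol | prohibited | permitted |
| Mesoridazine | prohibited | permitted |
| Thioridazine | prohibited | permitted |
| Pimozide | prohibited | not named |

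Listing 8 has 17 names under Antipsychotics. Listing 1 has 5 antipsychotics. The overlap is 4, so 4/17 of the permitted names and 4/5 of the banned antipsychotics are in conflict.

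**2. Look for other conflicts.** The generic names in prohibited Listings 1, 2 and 5 were matched against those in permitted Listings 6, 7 and 8, which gives nine pairings. Listing 1 with Listing 8 shares exactly these four names. The other eight pairings share none. Deleting the four rows therefore removes every name conflict found.

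**3. Decide which listing is wrong.** Section 9.4.7 bars QTc-prolonging drugs in both phases. Its stable-dose rule applies only to non-prohibited medication, and its allowance for on-study starts applies only to drugs not already barred. Exclusion criteria 25 and 37 point the same way. All of this agrees with Listing 1, so the Listing 8 entries are the error.

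**4. See whether anything in Appendix 2 resolves it.**

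- There is no statement of which listing prevails and no cross-reference from Listing 8 to Listing 1.
- The haloperidol comment in Listing 1 says when the risk rises. It does not confine the ban to intravenous or high-dose use.
- The invitation to contact the medical monitor covers cases where "investigators have any questions or concerns regarding any medication not listed that your" subjects may be taking. These four drugs are listed, twice.
- The general as-needed row in Listing 7 makes no exception for Listing 1 drugs.

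**5. Scheduled ECGs in the Extension Phase (Table 14).** ECGs fall at Visits 21, 25, 26, 28, 30, 32, 35 and 38, which are Months 0, 3, 6, 12, 18, 24, 36 and 48. The longest gaps are 156 − 104 = 52 weeks and 208 − 156 = 52 weeks. A drug started just after Month 24 or Month 36 could therefore run for up to 12 months before the next scheduled ECG.

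**The case against.** The strongest reply is that the body of the Protocol already settles the matter. Section 9.4.7 bars QTc-prolonging drugs outright, and the concomitant-medication footnotes of Table 7 (footnote j) and Table 14 (footnote l) send sites to that section, not to Listing 8. On this reading the defect is clerical. That is right about intent, and for that reason this is called a contradictory instruction and not an effective permission. It does not remove the problem, because Section 9.4.7 hands the naming of drugs to Appendix 2.

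Several points reduce the weight and stand:

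- Concomitant medication is reviewed at every Extension Phase visit. After Month 24 these visits fall at Weeks 104, 121, 139, 156, 173, 191 and 208, so the longest interval between reviews is 18 weeks. ECGs are also possible at unscheduled visits. The 52 weeks is a gap between scheduled ECGs and not a period without any oversight. Even so, a review that relies on Listing 8 would not flag the drug.
- The only QTcF signal reported for elenbecestat is a small rise of 14.9 msec at a single 800 mg dose (Section 7.2), which is 800/50 = 16 times the trial's highest dose. At 100 mg daily for 14 days no clinically significant ECG change was seen (Section 9.4.4).
- The trial randomizes about 60 (±20%) subjects, and exclusion criterion 6 removes many patients with psychiatric symptoms. Use of these drugs may be rare.
- The general row in Listing 7 names none of the four drugs. It is a secondary loophole and not a contradiction in itself.

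Exclusion criteria 25 and 37 do not close the gap. They act at Core Study entry and not on later starts, and the Extension Phase entry criteria in Appendix 6 test QTcF but do not repeat the exclusion for QT-prolonging medication.

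**Conclusion.** The concern holds. Listing 8 is wrong as written for four drugs, and sites are directed to the appendix that contains the error. It should be fixed because it is a safety instruction that contradicts itself in the current version, for both the Core Study and the Extension Phase. It is not a statistical flaw: no estimate, test or sample size depends on it, and no effect on results is claimed, since the Protocol gives no frequency of use for these drugs. The conclusion rests only on the Protocol's own text, namely the two listings, Section 9.4.7 and the exclusion criteria, and on no outside judgement about the drugs.

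**What to change.** 1. Delete chlorpromazine, haloperidol, mesoridazine and thioridazine from the Antipsychotics block of Listing 8.
2. Add one sentence to the introduction of Appendix 2: a drug in Listings 1 to 5 is prohibited even if it is named in, or falls under a general row of, Listings 6 to 8. This also closes the as-needed row in Listing 7.
3. Write to sites with the correction.

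The cost is four row deletions, one sentence and a letter. There is no change to design, data collection or analysis.
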